6.6.5. Exploratory Analysis

Exploratory endpoints will be analyzed analogously to primary and secondary endpoints with the same strategies for ICEs. Binary endpoints will be analyzed with a stratified test of risk difference and continuous endpoints will be analyzed with an MMRM model in general. Continuous data at timepoints before and including the primary timepoint will use all data from planned assessments up to and including the primary timepoint; continuous data after the primary timepoint will use all data from all planned assessments. Visit week, treatment group and interaction will be included in the MMRM model.

The number and proportion of subjects for binary endpoints in each treatment group will be reported, along with p-values, 95% CI without strata calculated using asymptotic Wald method will be reported as well. Results for continuous endpoints will presented as LS mean changes and associated SEs with associated 95% CI and p-values. For binary endpoints, a line plot showing the proportion of subjects experiencing such endpoints will be produced. For continuous endpoints, a line plot showing the LS mean and SE for each treatment group will be produced. Exploratory endpoint results will also be listed.

The following binary endpoints before or on Week 16 will be analyzed analogously to the primary endpoints of HiSCR75 at Week 16. The number and proportion of subjects for binary endpoints in each treatment group, p-values, 95% CI without strata calculated using asymptotic Wald method will be reported as well. The binary endpoints after week 16 will include number and proportion along with Clopper-Pearson 95% CI without strata according to the four randomized treatment groups. No p-value will be reported.

- HiSCR50, HiSCR75, HiSCR90 and HiSCR100 at Weeks 2, 4, 8, 12, 24 and 32;
- AN count of 0, 1, or 2 at Weeks 4, 8, 12, 24, and 32 among subjects with baseline Hurley Stage II;

- HS flares through Weeks 4 and 32;
- IHS4-55 response rates at Weeks 4, 8, 12, 16, 24 and 32;
- Draining fistula count of 0 at weeks 4, 8, 12, 16, 24 and 32
- Draining fistula count of 0 at weeks 4, 8, 12, 16, 24 and 32, among subjects with baseline draining fistula count of at least 1
- Draining fistula count of 0 at weeks 4, 8, 12, 16, 24 and 32, among subjects with baseline draining fistula count of at least 2
- Proportion with at least 3 points reduction from baseline in NRS in Patient Global Assessment of Skin Pain at its worst, among subjects with baseline NRS ≥ 4, at weeks 4, 8 12, 24 and 32. NRI will be handled analogously to the corresponding secondary endpoint analysis.
- \geq 50% reduction from baseline in total inflammatory lesion count (abscesses + inflammatory nodules + draining fistula) at Weeks 4, 8, 12, 16, 24 and 32
- \geq 50% reduction from baseline in draining fistula count (draining fistula alone)
- No increase in abscesses from baseline at Weeks 4, 8, 12, 16, 24 and 32

The following continuous endpoints before or on Week 16 will be analyzed with an MMRM model as specified in sec 6.6.4. LS mean changes and associated SEs with associated 95% CI and p-values will be presented. Model will include all data up to Week 16. The following continuous endpoints after Week 16 will be reported at all collected timepoints and be summarized according to the four randomized treatment groups. Mean values, mean changes and associated descriptive statistics along with 95% CI (for change from baseline) according to the four randomized treatment.

- Change of Modified Sartorius Score from baseline, Weeks 4, 8, 12, 16, 24, and 32;
- Change in PGA of Skin Pain (at its worst and average respectively) from baseline to Weeks 4, 8, 12, 16, 24, and 32;
 - If a subject received certain prohibited analgesic therapy within 28 days of the visit (including the day of the visit), the subject will be imputed as a non-responder (PGA of Skin Pain = 10) due to the ICE at the visit.
- Change in draining fistula count at Weeks 4, 8, 12, 16, 24 and 32;
- Change from baseline to Week 16 in EQ-5D;
- Change from baseline to Week 16 in DLQI;
- Change from baseline to Week 16 in HADS, HADS-anxiety, and HADS-depression;
- Change from baseline in IHS4 scores at Weeks 4, 8, 12, 16, 24, and 32

HS-PGA is an ordinal scale, as defined as below,

- Clear: No inflammatory or non-inflammatory nodules
- Minimal: Only the presence of non-inflammatory nodules

- Mild: < 5 inflammatory nodules or 1 abscess or draining fistula and no inflammatory nodules
- Moderate: < 5 inflammatory nodules or 1 abscess or draining fistula and ≥ 1 inflammatory nodules or 2 to 5 abscesses or draining fistulas and < 10 inflammatory nodules
- Severe: 2 to 5 abscesses or draining fistulas and \geq 10 or more inflammatory nodules
- Very severe: > 5 abscesses or draining fistulas

A shift table will be present by treatment to display the numbers of subjects change from baseline to Week 16. Data at Week 16 will be presented as observed data, and separately with missing data imputed using the last observed value before Week 16.

The HAD questionnaire comprises seven questions for anxiety and seven questions for depression. HADS will be summarized as HADS (total), HADS-anxiety, and HADSdepression respectively.

The EO-5D (3L) comprises the following five dimensions: mobility, self-care, usual activities, pain/discomfort, and anxiety/depression. Each dimension has 3 levels: no problems, some problems, and extreme problems. EQ-5D will be summarized as one utility score.

DLQI comprises 10 items arranged in six categories: symptoms and feelings (questions 1 and 2), daily activity (3 and 4), leisure (5 and 6), work or study (7), interpersonal relationships (8 and 9), and treatment (10). The total score can vary from 0 (no impact) to 30 (maximum impact).

SF-12 v2 questionnaire is an abbreviated version of the 36-Item Short Form Health Survey with 12 items in eight domains. Physical Component Score and Mental Component Score derived from the SF-12 v2 questionnaire will be summarized by treatment groups at baseline and each timepoint (Week 8, 16, and 32) with mean values and changes from baseline and associated 95% CI without further divided into Period 1 and 2.

The Patient Global Assessment of Skin Pain is collected as a daily diary, so the score used for analysis at visits prior to Week 16 will be the average of the scores recorded 6 days prior to and including the visit (7 days total for the average). For Patient Global Assessment of Skin Pain collected after Week 16, the value collected on the visit day will be used for analysis. No averaging will be done. If more than one value is collected at the visit, the first value collected will be used.

Erythema score at each visit will be listed.

6.6.6. Subgroup Analysis

Various subgroup analyses of the efficacy data will be reported. These analyses will investigate the treatment response within specific subgroups of interest, and assess whether the treatment response is consistent across different subgroup levels. All analyses will be Page 46 of 75 Final, Version 3.0, 03APR2024

ST-AD-008 version 06

performed on the FAS data set using methods analogous to those used for the primary analysis of that endpoint, defined above.

Summaries of these variables will be presented by subgroup:

- HiSCR50/75/90/100 at Week 16
- NRS in Patient Global Assessment of Skin Pain at its worst at Week 16 among subjects with baseline NRS \geq 4
- HS flare through Week 16
- Achieved AN count of 0, 1, or 2 at Week 16

The following subgroups are of interest:

- Race (White, Black or African American, other)
- Sex (male, female)
- Age (< $65, \ge 65$)
- Hurley stage at baseline (II, III)

The following subgroups are also of interest for HiSCR50/75/90/100 at Week 16:

- Geographic region
 - North America (US or Canada)
 - Europe (Spain, Hungary, Poland or Germany)
 - Non-US (Spain, Hungary, Poland, Germany or Canada)
- Country
 - o United States
 - o Canada
 - o Poland
 - o Hungary
 - o Spain
 - Germany
- BMI (≤ 18 , > 18 ≤ 25 , > 25 ≤ 30 , > 30 ≤ 35 , > 35)
- Smoking status (never, former, current)
- Prior biologic or JAK inhibitor (Any prior biologic or JAK inhibitor, any prior biologic, and prior TNF inhibitor, no prior biologic or JAK inhibitor)

Difference in response rate and 2-sided Mantel-Haenszel 95% CI will be reported for subgroup analyses for each endpoint similar to Section 6.6.1 and 6.6.3 using stratified tests. A forest plot for the difference in response rate and 2-sided 95% CI will also be presented No p-values will be reported for the subgroup analyses.

6.6.7. Post-Week 16 (Part B, Period 2) Additional Analyses

The following analyses will be done for all four randomized treatment groups in the FAS:

- Proportion with at least 3 points reduction from baseline in NRS in Patient Global Assessment of Skin Pain at its worst, among subjects with baseline NRS ≥ 4, at weeks 24 and 32 will be summarized by number and proportion along with Clopper-Pearson 95% CI without strata according to the four randomized treatment groups.
 - NRI will be handled analogously to the corresponding secondary endpoint analysis, except subjects who took Tramadol as allowed per-protocol (at a dose of up to 100 mg po every 4 hours, not to exceed 400 mg per 24 hours) during the 28 days prior to the visit will not be counted as a non-responder.
- Descriptive MMRM analyses will be performed by randomized treatment group, for the continuous endpoints described below. The measured value at the visit will be used as the response variable, with visit week, treatment, and treatment * visit week interaction included as predictors. The model will include all visits from Day 1 through Week 32. Unstructured covariance matrix will be used. Other variance-covariance matrices, such as autoregressive, and compound-symmetric will be considered if the model does not converge. Estimated LSMean, corresponding SE values, and 95% confidence intervals will be summarized at the timepoints defined below.
 - Modified Sartorius Score at Weeks 24 and 32;
 - NRS PGA of Skin Pain (at its worst and average respectively) at Weeks 24 and 32. To maintain consistency between all visits, only the score collected on the visit day will be used for this analysis.
 - Draining fistula count at Weeks 24 and 32;
 - EQ-5D at Weeks 24 and 32;
 - DLQI at Weeks 24 and 32;
 - HADS, HADS-anxiety, and HADS-depression at Weeks 24 and 32;
 - IHS4 scores at Weeks 24, and 32

These summaries will address the question of expected results if a subject is assigned to either 32 weeks of izokibep or 16 weeks of placebo followed by 16 weeks of izokibep.

- A time-to-event analysis using Kaplan-Meier (KM) curves by randomized treatment group will be created for the events listed below.). If estimable, quartiles of the time to each event will be summarized by randomized treatment group. Product limit estimate at Week 32 (Day 224) will be provided. Participants will be censored at the time of last recorded assessment on study:
 - First achievement of HiSCR75
 - First achievement of HiSCR100
 - First achievement of HiSCR90
 - First achievement of HiSCR50

- First achievement of AN count of 0, 1, or 2 for subjects with baseline Hurley Score II
- First achievement of ≥ 3 point reduction in NRS in Patient Global Assessment of Skin Pain at its worst among subjects with baseline NRS ≥ 4
 - To maintain consistency between all visits, only the score collected on the visit day will be used for this analysis.

These graphics will address the question of whether subjects originally randomized to placebo catch up in efficacy to the subjects who were randomized to izokibep by week 32.

The following analyses will be done by all four randomized treatment groups for the FAS subjects who had at least one dose of izokibep on or after Week 16. The analyses in subjects who received izokibep for the first 16 weeks will be done to address the question of whether responders/non-responders in the first 16 weeks of treatment experience subsequent sustained or added benefit in the following 16 weeks of treatment. The analyses in subjects who received placebo for the first 16 weeks will be done to evaluate if there is additional benefit after initial placebo response, or if placebo non-responders catch up to the subjects receiving 32 weeks of izokibep.

- The subgroup of subjects who were responders by HiSCR75 at Week 16 will be further evaluated by randomized treatment group at Week 24 and Week 32:
 - Response rate for HiSCR75, HiSCR100, HiSCR90, HiSCR50 will be summarized by randomized treatment group at Week 24 and Week 32. The responder proportions and Clopper-Pearson 95% CI without strata will be presented. The NRI approach to missing data will be the same as for the primary analysis.
 - Response rate for AN count of 0, 1, or 2 among those with Hurley stage II at baseline will be summarized by randomized treatment group at Week 24 and Week 32. The responder proportions and Clopper-Pearson 95% CI without strata will be presented. NRI approach will be the same as for the primary analysis.
 - Descriptive MMRM analyses will be performed by randomized treatment group, for change from baseline of IHS4 score and draining fistula count at Week 24 and Week 32. The change from baseline value will be used as the response variable, with baseline value, visit week, treatment, and treatment * visit week interaction included as predictors in the model. Estimated LSMean change from baseline, corresponding SE values, and 95% confidence intervals will be presented in the table summaries.

- The subgroup of subjects who were responders at Week 16 by AN count of 0, 1, or 2 (among those with Hurley stage II at baseline) will also be evaluated at Week 24 and Week 32 in the same manner as described for HiSCR75 responders.
- The subgroup of subjects who were non-responders at Week 16 by HiSCR75 will also be evaluated at Week 24 and Week 32 in the same manner as described for HiSCR75 responders.
- The subgroup of subjects who were non-responders at Week 16 by AN count of 0, 1, or 2 among those with Hurley stage II at baseline will also be evaluated at Week 24 and Week 32 in the same manner as described for the HiSCR75 responders.
- McNemar test will be used to evaluate the relationship between HiSCR75 response at Week 16 vs various response criteria at Week 32. P-values will be provided for descriptive purposes. The following response criteria at Week 32 will be used for this analysis:
 - o HiSCR75
 - o HiSCR90
 - HiSCR100
 - o HiSCR50
 - $\circ \quad \text{AN count of } 0, 1, \text{ or } 2$
- McNemar test will be used to evaluate the relationship between "AN count of 0, 1, or 2" response at Week 16 vs various response criteria at Week 32. P-values will be provided for descriptive purposes. The following response criteria at Week 32 will be used for this analysis:
 - o HiSCR75
 - HiSCR90
 - HiSCR100
 - HiSCR50
 - AN count of 0, 1, or 2

The following analyses will be done (by randomized treatment groups) for only the FAS subjects randomized to placebo who had least one dose of izokibep in Period 2 of the study AND who had a total AN count of \geq 5 at Week 16 and HS lesions present in at least 2 distinct anatomic areas (to correspond to the inclusion criteria), to address the question of how subjects respond to izokibep after 16 weeks of placebo, when they still meet original eligibility criteria:

- The baseline characteristics summary described in section 6.4.2 will be repeated for this analysis set at Week 16.
- The following binary endpoints will be analyzed analogously to the primary endpoint by randomized treatment group. The number and proportion of subjects for binary endpoints in each treatment group, 95% CI without strata calculated using asymptotic Wald method will be reported as well.
 - HiSCR50, HiSCR75, HiSCR90 and HiSCR100 calculated with respect to Day 1 at weeks 24 and 32;

HiSCR50, HiSCR75, HiSCR90 and HiSCR100 calculated with respect to Week 16 at weeks 24 and 32

HiSCR50/75/90/100 with respect to Week 16 is defined as meeting all three criteria below:

- (AN count at Week 16 AN count at current visit) / AN count at Week 16 \times 100% \geq 50/75/90/100%
- Abscess count at Week $16 \ge$ abscess count at the current visit
- Draining fistula count at Week 16 ≥ draining fistula count at the current visit
- AN count of 0, 1, or 2 at weeks 24 and 32 among subjects with baseline Hurley Stage II;
- AN count of 0, 1, or 2 at weeks 24 and 32 among subjects with Week 16 Hurley Stage II;
- HS flares from week 16 through 32, where HS flare is defined as proportion meeting the following two criteria at any assessment after Week 16 and at or before Week 32:
 - (AN count at current visit- AN count at Week 16) / AN count at Week $16 \times 100\% \ge 25\%$
 - AN count at current visit- AN count at baseline ≥ 2
- IHS4-55 response rates at weeks 24 and 32;
- Draining fistula count of 0 at weeks 24 and 32
- Proportion with at least 3 points reduction from baseline in NRS in Patient Global Assessment of Skin Pain at its worst, among subjects with Week 16 NRS ≥ 4, at weeks 24 and 32
- Descriptive MMRM analyses will be performed by randomized treatment group, for the continuous endpoints described below. The measured value at the visit will be used as the response variable, with visit week, treatment, and treatment * visit week interaction included as predictors. The model will include all visits from Day 1

through Week 32. Estimated LSMean, corresponding SE values, and 95% confidence intervals will be summarized. Line plots by treatment group will be produced:

- NRS Patient Global Assessment of Skin Pain (WORST). To maintain consistency between all visits, only the score collected on the visit day will be used for this analysis.
- Draining fistula count, Modified Sartorius Score, IHS4 Score, HS-PGA score, all HADS scores (Total, Anxiety, Depression), EQ-5D Utility Score and DLQI Total Score.

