Exploratory biomarker sampling ^m		X				X	X					X						X		
Treatment Assignment																				
Treatment assignment/Randomization		X																		
Study drug administration and Diary	d Dosing																			
QW dosing (at site) ^{a, n}		X	X	X	X	X	X	X	X	X	X	X	X		X	X	X			
Q2W dosing (at site) ^{a, n}		X		X		X	X	X		X		X		X	X	X	X			
Dosing diary ^o																		→		

ADA = anti-drug antibody; AE = adverse event; AN = abscess and inflammatory nodule; d = day; CRF = case report form; C-SSRS = Columbia-Suicide Severity Rating Scale; DLQI = Dermatology Life Quality Index; ECG = electrocardiogram; EOS = end of study; EQ-5D = European Quality of Life 5-dimension;

ET = early termination; HADS = Hospital Anxiety and Depression Scale; HBsAg = hepatitis B surface antigen, HCV = hepatitis C virus; HS-PGIC = HS Patient Global Impression of Change; NRS = Numeric Rating Scale; PGA = Physician's Global Assessment; PK = pharmacokinetic; PPD = purified protein derivative; Q2W = every other week; QW = once weekly; SAE = serious adverse event; SF-12 = 12-Item Short Form Survey; TB = tuberculosis; WOCBP = women of childbearing potential.

- ^a Visit/dosing windows of ±3 days on either side of the scheduled visits/dosing are permitted; however, the investigator should try to keep the subjects on the original visit/dosing schedule. In case of a delayed or missed dose, the investigator should return subjects on the original visit/dosing schedule in relation to Day 1 for subsequent doses. The window of ± 3 days is relative to Day 1 and applicable for all subsequent visits/dosing. For QW dosing, the time between doses should be no less than 4 days and no more than 10 days. For Q2W dosing, the time between doses should be no less than 11 days and no more than 17 days. Study visits for QW dosing are not required at Weeks 5 to 7, 9 to 11, 18, 19, 21 to 23,25 to 27, or 29 to 31 if subject/caregiver completes study drug administration at home. Subjects randomized to Q2W arms are not required to complete visits on Weeks 1, 3, 13, 15, and 17. Study visits for Q2W dosing not required at Weeks 6, 10, 22, 26, or 30 if subject/caregiver completes study drug administration at home. See footnotes n and o below.
- ^b The follow-up period consists of 2 visits to be completed by all subjects at Week 39 and Week 45. For subjects who early terminate, the follow-up visits should be completed 8 weeks (± 5 days) and 14 weeks (± 5 days) after the last dose of study drug.

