- ^c Vital signs include measurements of temperature, respiratory rate, systolic and diastolic blood pressure, and pulse. Measurements should be taken in a sitting position after 5 minutes of rest.
- d Electrocardiograms in triplicate will be recorded after subject has been supine for at least 5 minutes.
- ^e Chest x-ray (posterior/anterior or anterior/posterior) will be performed at screening for subjects who do not have a chest x-ray available within 3 months of screening. Women of childbearing potential must have negative pregnancy test before x-ray is performed.
- f Serious adverse events will be recorded from the signing of informed consent through the 8-week follow-up visit (ie, 8 weeks after the last dose of study drug); adverse events will be recorded from Day 1 (ie, administration of study drug) until 4 weeks after the last dose of study drug.
- ^g Confirm ongoing antiseptic wash requirement at every visit. From Screening through Week 16, subjects will complete a daily diary of their analgesic use. From Week 16 through Week 32, subjects will be required to tell site staff if they took any analgesics within 24 hours of their site visit. See Section 10.10. Subjects will refrain from taking analgesics 12 hours before the site visit, if possible.
- ^h Lesion count will be performed at every study visit marked in the Schedule of Activities and must address all relevant anatomical regions in each subject. The AN count includes counts of draining tunnels (fistulas and sinuses). See Section 8.1.1 for more details. Any unscheduled visit for disease worsening based on the investigator judgment will include AN count and will be recorded in the appropriate CRF.
- ¹From screening through Week 16, subjects will complete a daily diary of their skin pain. See Section 8.1.5. No in-site assessment of skin pain will be completed at the Week 16 visit. From Week 16 through Week 32, subjects will complete skin pain assessments at the site. Note: subjects may not be randomized if pain diaries are not completed for ≥ 3 out of 7 days (at a minimum) prior to the Day 1 visit.
- ^j For subjects who consent to the optional photography substudy at selected sites, photographs will be taken.
- ^k QuantiFERON® test or PPD test for TB will be performed. Note: T-SPOT® testing may be allowed after consultation with medical monitor.
- ¹Serum pregnancy test required for screening and urine pregnancy test required at all other times for women of childbearing potential.

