Part B is a randomized, double-blind, placebo-controlled, parallel group, dose-finding investigation to evaluate the efficacy, safety, and immunogenicity of izokibep in subjects with moderate to severe HS. Subjects will complete up to a 28-day screening period, followed by a 16-week double-blind treatment period. At completion of the Week 16 visit procedures, subjects randomized to placebo will be switched to active treatment in a blinded manner for the Week 16 dose through Week 30 (Q2W dose group) or Week 31 (QW dose group). Subjects randomized to izokibep will remain on the same dose through Week 30 (Q2W dose

group) or Week 31 (QW dose group). After their respective treatment periods, all subjects will enter a follow-up period that includes 2 visits to be completed at Week 39 and Week 45. For subjects that early terminate the follow-up visits should be completed 8-weeks (\pm 5 days) and 14 weeks (\pm 5 days) after the last dose of study drug.

Approximately 170 subjects will be randomized into 1 of 4 groups in a 1:1:2:2 ratio as follows:

- Group 1 (n = 28-29): placebo SC QW from Day 1 (Week 0) to Week 15, then izokibep SC 160 mg QW from Week 16 to Week 31.
- Group 2 (n = 28-29): placebo SC Q2W from Day 1 (Week 0) to Week 14, then izokibep SC 160 mg Q2W from Week 16 to Week 30.
- Group 3 (n = 56-57): izokibep SC 160 mg QW from Day 1 (Week 0) to Week 31.
- Group 4 (n = 56-57): izokibep SC 160 mg Q2W from Day 1 (Week 0) to Week 30.

Randomization will be stratified by any prior biologic/Janus Kinase (JAK) inhibitor used for HS (Yes/No) and Hurley Stage (II or III).

Subjects will complete study assessments according to the study visits outlined in the SoA in the protocol. Day 1 corresponds to the first dose of study drug. All subsequent visits will be scheduled based on the Day 1 visit.

Subjects in the QW dosing groups (Group 0 [Part A], Groups 1 and 3 [Part B]) will have study visits at screening, Day 1 (Week 0), and at Weeks 1, 2, 3, 4, 8, 12, 13, 14, 15, 16, 17, 20, 24, 28, and 32 as well as at the follow-up visits.

Subjects in the Q2W dosing regimens (Groups 2 and 4 in Part B) will have study visits at screening, Day 1 (Week 0), and at Weeks 2, 4, 8, 12, 14, 16, 18, 20, 24, 28, and 32 as well as at the follow-up visits.

Subjects assigned to placebo SC QW and placebo SC Q2W will be grouped into a single placebo group for comparison to each dosing regimen of izokibep for Part B. The primary endpoint will be assessed at Week 16.

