5.1. Time Points and Visit Windows

5.1.1. General Definitions

All assessment days will be related to the first day of the first dose of the study drug.

Day 1 is defined as the date of the first dose of the study drug. Relative days after Day 1 are calculated as (assessment date – Day 1 date) + 1. Relative days prior to Day 1 are calculated as (assessment date – Day 1 date). The day prior to Day 1 is Day -1. There is no Day 0.

The date of the first dose of study drug for each subject will be taken from the Study Drug Administration CRF page. If the date in this CRF page is missing, alternatively the date of enrollment/randomization will be used.

The date of the last dose of study drug for each subject will be taken from the Study Drug Administration form, with the last study drug administration date from any visit used as the date of last study drug.

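### The Week 32 Kaplan-Meier estimate in SAP 6.6.7 is read at Day 224, one day before the Week 32 visit is due under the SAP's own day count, and the time scale is not stated

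*SAP*

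**What the plan says.** SAP 6.6.7 plans Kaplan-Meier curves by randomized group for six first-achievement events in Part B: HiSCR75, HiSCR100, HiSCR90, HiSCR50, AN count of 0, 1 or 2 (baseline Hurley Stage II), and a pain reduction of at least 3 points (baseline NRS of 4 or more). It adds "Product limit estimate at Week 32 (Day 224) will be provided" and, as the censoring rule, "Participants will be censored at the time of last recorded assessment on study". The graphics are meant to show "whether subjects originally randomized to placebo catch up in efficacy to the subjects who were randomized to izokibep by week 32".

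SAP 5.1.1 fixes the day count. The first dosing date counts as Day 1, there is no Day 0, and the rule for later dates is "Relative days after Day 1 are calculated as (assessment date – Day 1 date) + 1". SAP 2.1 says "All subsequent visits will be scheduled based on the Day 1 visit". Footnote a to the protocol's Schedule of Activities (1.3) sets the tolerance: "The window of ± 3 days is relative to Day 1 and applicable for all subsequent visits/dosing".

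Footnote h to the same schedule says "Lesion count will be performed at every study visit marked in the Schedule of Activities"; after Week 16 the marked visits are Weeks 24, 28 and 32. The pain event in 6.6.7 uses only the score collected on the visit day, and the last scheduled pain score before Week 32 is also at Week 28.

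SAP 5.1.4 states a general rule that data are analysed by nominal study visit. SAP 6.6.7 does not say whether its Kaplan-Meier time is nominal visit or actual study day.

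**The concern.** These events are not observed continuously. Apart from unscheduled visits, a first response can be recorded only on an assessment day. Between the end of the Week 28 window and the start of the Week 32 window nothing is scheduled that could produce an event. The curve is therefore flat and then steps at the Week 32 visit, and a read-out at Day 224 cuts through that step.

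A one-day difference in labelling would be trivial for an event that can start on any day. Here it decides whether a subject seen exactly on schedule is counted. Six events in four randomized groups give 24 estimates labelled Week 32, each of which could leave out part or all of what the Week 32 visit found. A tabulated value could also disagree with the curve beside it if the curve is drawn past Day 224.

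**Working it through.** **Inputs.** Day 1 is first dose, and later days are date difference plus 1 (SAP 5.1.1). Visits are scheduled from Day 1 (SAP 2.1), with a window of ±3 days (Protocol 1.3, footnote a). The read-out is Day 224 (SAP 6.6.7). The distribution of actual visit days is not in the documents, so it is assumed and varied below.

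**1. The plan's figure.** 32 × 7 = 224. Day 224 is reproduced as elapsed days without the added 1, or as nominal week times seven. It is not reproduced by the SAP's study-day formula, which gives 32 × 7 + 1 = 225.

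**2. Windows.** Week 28: 28 × 7 + 1 = 197, so Days 194 to 200. Week 32: 225 ± 3, so Days 222 to 228.

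**3. Share of Week 32 first responses omitted on the actual-day scale.** This is the share of in-window visits on Day 225 or later, taking visit day as unrelated to response:

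| Assumed timing of Week 32 visits | Omitted |
|---|---|
| All on Day 225 | 100% |
| Skewed late (weights 1,1,1,2,3,3,3 over Days 222 to 228) | 11/14 = 79% |
| Half on target, the rest even | 75% |
| Triangular (weights 1,2,3,4,3,2,1) | 10/16 = 62.5% |
| Even over the window | 4/7 = 57% |
| Skewed early (weights 3,3,3,2,1,1,1) | 5/14 = 36% |
| All on Days 222 to 224 | 0% |

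Any timing symmetric about Day 225 loses at least half. On other time scales the answer changes: elapsed days without the added 1 would lose 3/7 = 43% under even spread, and nominal week times seven would lose none.

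**4. Illustration (assumed inputs).** Suppose 40% have responded by Week 28 and 10% of the remaining 60% first respond at Week 32. The full Week 32 value is 40 + 0.10 × 60 = 46%.

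- All visits on target: Day 224 gives 40%.
- Even spread, non-responders censored after the window: 40 + 6 × 3/7 = 42.6%.
- Even spread, non-responders censored at their Week 32 assessment: 1 − 0.60 × (1 − 0.1/7)(1 − 0.1/6)(1 − 0.1/5) = 43.0%.

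**5. Would a later day repair it?** Same assumptions, even spread:

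- Day 225, censoring after the window: 40 + 6 × 4/7 = 43.4%. Visits on Days 226 to 228 are still missed.
- Day 228, censoring after the window: 46%, which is correct.
- Day 228, non-responders censored at their Week 32 assessment: the risk set shrinks day by day, so the survival factor is the product of (1 − 0.1/j) for j = 7 down to 1, which is 0.7655. The estimate is 1 − 0.60 × 0.7655 = 54.1%, about 8 points too high.
- Nominal visit for events and censoring, events first: 1 − 0.60 × 0.90 = 46%, whichever censoring reading applies.

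**6. Effect on the gap between groups.** Let m be the omitted share, and let ΔI and ΔP be the increments at Week 32 for izokibep and placebo. With the same visit timing in both groups and censoring after the window, the reported gap (izokibep minus placebo) equals the true gap minus m × (ΔI − ΔP). Equal increments leave it unchanged; otherwise the sign depends on which increment is larger. The documents give neither.

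**The case against.** The best defence is that SAP 5.1.4 already makes nominal visit the rule for all data, with no exception for these curves. The label then simply means week times seven and no response is lost. This cannot be excluded. But 6.6.7 names a day and censors at a time of assessment. The one Kaplan-Meier time scale the SAP writes out, for Period 2 safety events in 6.7.2, is a date difference plus 1, in a section that uses the same Day 224 label. A programmer could reasonably follow either route, and only one gives a Week 32 figure.

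Three further points stand. The catch-up question is assigned to the graphics, and nothing stops the curves at Day 224. Response rates at Week 32 by randomized group are planned in 6.6.5 and 6.6.7, so the visit's results are not lost, although response at that visit is not cumulative first achievement. And this is a descriptive Period 2 analysis.

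A reader might infer that the estimate is in effect a Week 28 result. That is exact only if no one attends on Days 222 to 224, which the window allows. A reader might also infer a bias against placebo catching up. That requires placebo switchers to be gaining first responses faster than continuous izokibep subjects between Weeks 28 and 32, and the documents contain no such figures.

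**Conclusion.** The concern holds in a limited form. Day 224 conflicts with the SAP's own day formula, which puts the Week 32 visit on Day 225, and the time variable for these curves is undefined. On an actual-day scale the tabulated estimate drops all Week 32 first responses if visits are on target, 57% if they are evenly spread, and fewer if they run early. The day arithmetic is certain. The size of the loss rests on visit timing and on the time scale chosen, neither of which is given.

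Only subjects whose first response falls at Week 32 are affected. The documents support neither a claim that the estimate always reverts to Week 28 nor a claim about the direction of bias between groups. No primary, secondary or alpha-controlled result is touched.

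**What to change.** State in SAP 6.6.7 that, for these visit-assessed events, both event time and censoring time are the nominal visit week, consistent with SAP 5.1.4. Report the product-limit estimate at the nominal Week 32 visit, with events ordered before censorings at the same visit, and drop the Day 224 label there.

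Do not simply move the read-out to Day 225, which still misses late visits. Do not move it to Day 228 on an actual-day scale either, because that can overestimate if non-responders are censored at their Week 32 assessment within the window.

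The cost is a sentence or two in the SAP and a change to the time variable in the program. No data collection changes.
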